2.1.4.4 Vital signs variables

Vital signs include blood pressure and pulse (assessed after 5 min in supine position) and weight.

2.1.4.5 Physical examination variables

Physical examination includes the following body systems:

- General appearance
- Head, eyes, ears, nose, throat
- Central and peripheral nervous system
- Respiratory
- Cardiovascular
- Gastrointestinal
- Musculoskeletal
- Skin
- Lymph node palpation
- Other

2.1.4.6 Immunogenicity variables

Antibodies to caplacizumab will be evaluated in blood samples collected from all participants as specified in the protocol. In case of a severe and/or serious hypersensitivity reaction, judged to be related to study drug, an additional blood sample will be collected as soon as possible after the start of the event to characterize the reaction.

2.1.5 Pharmacokinetic variables

Pharmacokinetic variable includes the caplacizumab concentration in case of treatment with the IMP.

2.1.6 Pharmacodynamic endpoints

Pharmacodynamic parameters include vWF:Ag concentration and RICO activity (in case of recurrence and treatment with the IMP).

2.2 DISPOSITION OF PATIENTS

This section describes patient disposition for both patient study status and the patient analysis populations.

Enrolled participants are defined as all participants who signed the inform consent form [ICF].

For patient study status, the total number of patients in each of the following categories will be presented in the clinical study report, in summary table for the Intention to Observe [ITO] and recurrence populations (see [Section 2.3](#) for more details on the populations):

- Enrolled patients
- Patients with a recurrence
- Patients with a recurrence and not treated with IMP
- Patients with a recurrence and treated with IMP
- Patients who completed the study
- Patients who discontinued the study, with the primary reason
- Status at last study contact
- Lost to follow-up

For all categories of patients (except for the enrolled) percentages will be calculated using the number of exposed patients divided by the number of patients enrolled patients as the denominator. Reasons for treatment discontinuation will be supplied in tables giving numbers and percentages by analysis group.

A patient is considered lost to follow-up under the following circumstances:

- A patient missed 2 consecutive 6-monthly follow-up visits and did not reply to site staff contact attempts;
- The site contacted the patient at least three times before each of the 6-monthly visits without success, and all contact attempts were documented in the source documents;
- A certified letter was sent to the patient (where possible following site/country procedure/regulations) before the second visit last planned date to inform the patient that if

the second visit would be missed the patient would be withdrawn from the trial without access to future IMP treatment.

All critical or major deviations potentially impacting efficacy analyses, and drug-dispensing irregularities, and other major or critical deviations will be summarized in tables giving numbers and percentages of deviations by treatment group.

Trial termination data including reason for completion/discontinuation, the number of days since screening, date of first study drug intake and date of last study drug intake at trial termination will be listed.

- A tabulation of the number and percentage of participants by analysis period, subperiod, and time point will be given for the recurrence population and the ITO population.
- The following 3 dates will be presented on the enrolled participants.
 - Date of the first signature on the ICF
 - Last visit date (all visit; including unscheduled visits)
- A descriptive statistics of the analysis period duration will be provided by phase, analysis period on the ITO and Recurrence population. Analysis period including start and end dates, and duration of each analysis period will be listed. The duration (days) is derived as follows:
 - Period end date – period start date + 1
- A tabulation of the number and percentage of participants in each of the analysis populations will be provided.

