Daily s.c. administration of 10 mg study drug will continue for a period of 30 days after stop of daily PE. No adjustment to this period will be made for tapering of PE. Subjects (and/or caregivers) will be trained on preparing and administering caplacizumab and are to administer the study drug after discharge from the hospital.

Treatment extension period

Treatment with caplacizumab beyond these 30 days will be guided by a number of risk factors for relapse of the presenting TTP episode and may be accompanied by an optimization of the immunosuppressive treatment. The risk factors will include the ADAMTS13 activity profile, as well as other signs and symptoms of continued underlying disease activity, such as presence of inhibitors if measured as routine practice by the site. Continued caplacizumab treatment should be given for additional 7-day periods with a maximum of 28 days for subjects whose ADAMTS13 activity profile remains below 10% based on weekly measurements and/or exhibit other clinical signs or symptoms of underlying disease. caplacizumab treatment should be stopped when ADAMTS13 activity shows a sustained upward trend of >10% and/or when there is an improvement in other signs and symptoms of underlying disease activity and at the latest on Day 28 of the study drug treatment extension period.

Estimated Study Duration

The anticipated study duration per subject is approximately 3 years. The end of the study is defined as the last visit of the last subject participating in the study.

^{§§} Pregnant subjects or those with a history of a severe and/or serious hypersensitivity reaction to caplacizumab may participate in the study but will not receive treatment with caplacizumab. Also, treatment with caplacizumab may not be initiated for subjects who did not have a baseline visit.

^{***} Up to 1 PE (which may be spread over 2 or more sessions in 24 hours) may be given prior to initiation of treatment with caplacizumab as long as considered part of the PE for the treatment of the presenting TTP episode.

Determination of Sample Size

The sample size is not based on statistical considerations but rather on the number of subjects who complete Study ALX0681-C301 (HERCULES) and accept the option to participate in this FU study (ALX0681-C302). All subjects who enrolled in this FU study will be included in the safety and efficacy analyses.

Independent Data and Safety Monitoring Board (DSMB)

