3.2.1. INCLUSION CRITERIA

Each potential subject must satisfy all of the following criteria to be enrolled in the study:

1. Completed the Final (28 day) FU visit in Study ALX0681-C301.
2. Is ≥ 18 years of age at the time of signing the informed consent form (ICF).
3. Provided informed consent prior to initiation of any study specific activity/procedure.

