3.3.2. RANDOMIZATION

Not applicable. This is a FU study for subjects who completed Study ALX0681-C301. Upon a recurrence of TTP, subjects will receive open-label treatment with caplacizumab in addition to standard of care.

After obtaining oral and written informed consent, subjects will be screened according to the inclusion and exclusion criteria and will receive a unique subject identification (ID) number.

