3.6. STATISTICS

3.6.1. STUDY POPULATIONS

The following populations will be considered for analysis:

- **Intention-to-observe (ITO) population:** All subjects who enrolled in Study ALX0681-C302.
- **Recurrence population:** All subjects in the ITO population who have experienced at least one recurrence in Study ALX0681-C302.

Unless otherwise specified, the ITO population will be used for the analysis of the Q6M FU data on efficacy, disease-related markers, PD, immunogenicity and safety. The recurrence population will be used for analysis of data collected during recurrence periods. Depending on whether subjects have been treated with caplacizumab or not, or have been retreated with caplacizumab, different subsets of the recurrence population may be defined for specific analyses. This will be detailed in the statistical analysis plan (SAP).

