2.1.3.5 Other efficacy endpoints

2.1.3.5.1 TTP-related events

TTP related event is defined as:

- TTP-related death,
- recurrence of TTP
- or reported major thromboembolic event [e.g., myocardial infarction, cerebrovascular accident, pulmonary embolism or deep venous thrombosis] based on SMQ based on the SMQ ‘Embolic and thrombotic events (arterial, venous, and vessel type unspecified and mixed arterial and venous)’.

2.1.3.5.2 Time to TTP-related events:

The time to TTP related event (in days) is defined as the date from screening/baseline visit to the date of the first TTP related event. Patients without an event during the ALX0681-C302 study are censored at the end of the study.

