2.3 ANALYSIS POPULATIONS

2.3.1 Intention-to Observe (ITO) Population

All subjects who enrolled in study ALX0681-C302. Unless otherwise specified, the ITO population will be used for the analysis of the Q6M FU data on efficacy, disease-related markers, PD, immunogenicity and safety.

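### The SAP's consent-only definition of enrolled is wider than the protocol's, ITO subjects without a baseline visit have no time origin in two Kaplan-Meier analyses, and the disposition percentage rule names the wrong numerator

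*SAP*

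**What the plan says.** **Who is enrolled.** SAP 2.2: "Enrolled participants are defined as all participants who signed the inform consent form". SAP 2.3.1 then defines ITO as "All subjects who enrolled in study ALX0681-C302", and Protocol 3.6.1 has the same wording: "All subjects who enrolled in Study ALX0681-C302". Protocol 3.2.1, however, says "Each potential subject must satisfy all of the following criteria to be enrolled in the study". Consent is one of its three inclusion criteria, and Protocol 3.2.2 adds two exclusion criteria. Protocol 3.3.2 gives the order: "After obtaining oral and written informed consent, subjects will be screened according to the inclusion and exclusion criteria".

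**Subjects without a baseline visit.** A footnote in Protocol 3.1.1 says "treatment with caplacizumab may not be initiated for subjects who did not have a baseline visit"; Protocol 3.3.1 repeats this. Neither place removes such subjects from the study or from ITO. SAP 2.1.3.5.2 has time to TTP-related event "defined as the date from screening/baseline visit to the date of the first TTP related event", and SAP 2.1.3.5.6 uses the same start for major thromboembolic events.

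**Disposition percentages.** For every category except the enrolled row, SAP 2.2 says "percentages will be calculated using the number of exposed patients divided by the number of patients enrolled patients as the denominator". The table is planned for both the ITO and the recurrence population.

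**The concern.** One word, enrolled, defines the main analysis population and means different things in the two documents. A person who signs consent and then fails screening is not enrolled under the protocol but belongs to the SAP's ITO. SAP 1.6, which lists the SAP's statistical modifications, does not mention this change.

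An ITO subject with no baseline visit raises a different problem. Two Kaplan-Meier analyses need a date that this subject lacks, and no rule covers the case. The crude percentages and those curves could then describe different people under one ITO label.

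The disposition rule would misstate the percentages in the table that readers need to assess attrition over three years of voluntary follow-up, in a study whose efficacy data are analysed as observed without imputation (SAP 2.4.4).

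**Working it through.** The documents give no sample size calculation and no count of screen failures, so there is no stated figure to reproduce. The check compares definitions, then uses ratios with assumed counts.

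**1. Enrolled and ITO**

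| Subject | Protocol | SAP |
|---|---|---|
| Signed, eligible, baseline visit done | enrolled, ITO | enrolled, ITO |
| Signed, eligible, no baseline visit | enrolled, ITO | enrolled, ITO |
| Signed, fails a criterion | not enrolled | enrolled, ITO |

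Only the third line differs. SAP 2.4.5.1 takes the population in each treatment group as the denominator for adverse event percentages, so these subjects would count there. On a plain reading they also count in the ITO event percentages of SAP 2.4.4.1 to 2.4.4.3, because having no reported event is not a missing value.

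Size, for illustration. Inputs: N = 92 signers (the approximate planned size of the parent study, Protocol 1.2.4); p = 18% (the median recurrence incidence from the literature in Protocol 1.1); k = number of screen failures, assumed to have no event. Printed percentage = p × (N − k)/N.

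| k | Calculation | Printed |
|---|---|---|
| 0 | 18% × 92/92 | 18.0% |
| 2 | 18% × 90/92 | 17.6% |
| 5 | 18% × 87/92 | 17.0% |
| 9 | 18% × 83/92 | 16.2% |

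With eligible subjects only in the denominator, each line gives 18.0%.

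**2. Time origin**

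- Time to TTP-related event and time to major thromboembolic event both start at the screening/baseline visit. They are undefined without that visit.
- Time to first recurrence starts at the end of the previous episode in the parent study (SAP 2.1.3.5.5). It is not affected.
- SAP 2.1.4 starts the on-study period at consent, while Table 3 in SAP 2.5.4 starts the observation phase at the screening/baseline visit. The SAP therefore supplies no single fallback date.

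**3. Disposition rule**

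Eight categories are listed and the enrolled row is excepted, leaving seven. Exposed is not defined in SAP 2.2; SAP 2.4.3 uses exposure for study drug given in the recurrence population. Assume 92 enrolled, 17 with a recurrence, 15 of them treated, and 70 completers.

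| Row | Rule as written | Own count |
|---|---|---|
| Recurrence | 15/92 = 16.3% | 17/92 = 18.5% |
| Recurrence, not treated | 15/92 = 16.3% | 2/92 = 2.2% |
| Recurrence, treated | 15/92 = 16.3% | 15/92 = 16.3% |
| Completed | 15/92 = 16.3% | 70/92 = 76.1% |

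The remaining three rows would also print 16.3%. In the recurrence-population table the denominator is wrong as well: the treated row should be 15/17 = 88.2%, not 15/92 = 16.3%.

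**The case against.** **The affected group may be empty.** Protocol Table 1 puts consent, eligibility review and baseline assessments at the same visit, and the criteria are few. Nothing shows that anyone signed and then failed. This stands, and it limits the size of the first part to an illustration.

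**A reader might infer that every ITO percentage is diluted by people who were never followed.** The documents do not support that. SAP 2.4 drops missing values from categorical denominators, and change-from-baseline summaries cannot include someone without a baseline. Subjects without a baseline visit are not necessarily event-free either. Adverse events are collected from consent (Protocol 3.4.9.1), and on a recurrence such subjects follow the schedule without caplacizumab, with a recurrence visit and a follow-up visit (Protocol 3.1.1, Appendix 1). The bar on drug becomes relevant only when such a subject has a recurrence, which is itself an event.

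**A reader might also infer that ITO should require a baseline visit.** The protocol does not make that visit a condition of enrolment. It ties its absence only to drug treatment and includes all enrolled subjects in the safety and efficacy analyses. Adding the condition would depart from the protocol and could remove recurrences from ITO.

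**The numerator is a drafting slip that a programmer would notice.** Probably so: the sentence is garbled, correct counts would print beside the percentages, and SAP 2.2 also plans tabulations by period and time point. But it is the only percentage rule given for the table, and it is wrong as written.

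**Conclusion.** The point holds in three limited parts.

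- The SAP's enrolled is wider than the protocol's, and the difference carries into ITO without being declared. The numerical effect is unknown and may be zero. The fall from 18.0% to 16.2% rests on assuming 9 event-free screen failures among 92 signers.
- ITO subjects without a baseline visit belong in ITO under both documents. The defect is the missing rule for two Kaplan-Meier analyses, not their inclusion.
- The disposition rule is wrong for six of the seven rows it covers, and its denominator does not suit the recurrence population. This does not depend on whether any screen failure exists.

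The analyses are descriptive with no formal tests (SAP 2.4.4.8), so no error rate or power is affected. General dilution of mortality, adverse event and event results is not shown.

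**What to change.** 1. In SAP 2.2 and 2.3.1, define enrolled, and hence ITO, as consent signed and Protocol 3.2 eligibility confirmed. Do not add a baseline-visit condition.
2. Show consented-but-not-enrolled subjects on a separate disposition row and list any known events in them.
3. For ITO subjects without a baseline visit, state in SAP 2.1.3.5.2 and 2.1.3.5.6 either a time origin (for example the consent date, where the on-study period starts) or an exclusion rule with the number excluded.
4. Replace the percentage rule in SAP 2.2 with the number of patients in the category divided by the number in the relevant population, ITO or recurrence.

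The cost is SAP wording and matching table specifications; no new data are needed. Whether any event percentage moves, and in which direction, depends on how many screen failures exist and whether any of them has a recorded event.

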2.2.1 Drug dispensing irregularities

Drug-dispensing irregularities will be monitored throughout the study and reviewed on an ongoing basis. All drug-dispensing irregularities will be documented in the clinical study report.

2.3 ANALYSIS POPULATIONS

2.3.1 Intention-to Observe (ITO) Population

All subjects who enrolled in study ALX0681-C302. Unless otherwise specified, the ITO population will be used for the analysis of the Q6M FU data on efficacy, disease-related markers, PD, immunogenicity and safety.

2.3.2 Recurrence population

All subjects in the ITO population who have experienced at least one recurrence in study ALX0681-C302. The recurrence population will be used for analysis of data collected during recurrence periods.

2.4 STATISTICAL METHODS

For continuous parameters, descriptive statistics will be presented when $n \geq 2$. When $n = 1$, only sample size (n) and mean, i.e. the value itself, are shown. Descriptive statistics will include the number of non-missing data points (n), the arithmetic mean, the standard deviation (SD) (for baseline summaries) or standard error (SE) (for post-baseline, change from baseline, or percentage change summaries), the median, minimum and maximum.

For categorical parameters, frequency tabulations are prepared, consisting of frequency counts (non-missing observations) and percentages. Missing values will not be included in the denominator count when computing percentages.

Descriptive statistics of PK concentrations and PD data will additionally include 5% and 95% percentiles, SD of arithmetic mean, coefficient of variation (CV)% of arithmetic mean, geometric mean and geometric SD.

For the graphs showing mean values or percentages, an SE flag will be shown. For PK graphs showing geometric mean values, a geometric SD flag will be shown.

- Change from baseline and percentage change from baseline
- The change from baseline will be calculated for all post-baseline time points as:
- Change from baseline at time point $t = \text{value at time point } t - \text{baseline value}$.
- Percentage change from baseline at time point $t = 100 * \frac{[\text{value at time point } t - \text{baseline value}]}{\text{baseline value}}$.
- Change from baseline and percentage change from baseline will be calculated separately for each of the analysis periods from their respective baseline values.

Relative number of days

The relative day (DY) is calculated as follows:

- Visit date – reference date + 1 day, when the visit date is on or after the reference date
- Visit date – reference date, when the visit date is before the reference date.

The reference date is the date of first intake of the study drug, which by definition has DY=1. There is no DY=0.

2.4.1 Demographics and baseline characteristics

Demographic and baseline data will be evaluated descriptively. Summaries will be presented on the ITO population and each recurrence episode on the Recurrence population separately. Baseline disease characteristics will be evaluated descriptively and will be presented for the Recurrence population for each of the recurrence episode. Parameters are described in [Section 2.1.1](#).

Demographic and baseline data, baseline characteristics, screening tests of pregnancy test and creatinine assessment, medical history, concomitant diseases, and ADAMTS13 activity will be listed. Separate listings will be presented for general medical history and for TTP history.

2.4.2 Concomitant medications

Concomitant medications will be presented for the ITO and recurrence populations.

Based on their start and stop date, prior and concomitant therapies will be reported in each analysis period during which they were applied. This implies that each therapy can be reported more than once.

For the ITO population, concomitant medication will be presented for the overall study period.

For the recurrence population, concomitant therapies will be tabulated by generic term and by phase, analysis period and subperiod. Multiple records of the same generic term for the same participant will be counted only once. The table will therefore present participants, not occurrences. The tables are sorted by decreasing frequency. Immunosuppressive (including rituximab) and non-immunosuppressive concomitant therapies will be tabulated separately. A separate tabulation by analysis period will be made to summarize the number and proportion of participants who received concomitant antithrombotic therapies (Anatomical therapeutic chemical classification system (ATC) codes starting with B01A) and the number and proportion of participants to whom transfusions have been given.

The duration of corticosteroids use and the cumulative dose of corticosteroids during the overall treatment period will be summarized for the recurrence population.

Different types of corticosteroids will be converted to Prednisolone equivalent doses before calculating the cumulative dose of corticosteroids. The cumulative dose will be given in mg/day (Please refer to [Appendix B](#) or more details).

Prior and concomitant therapies will be listed including coding information. Plasma exchange will also be listed.

2.4.3 Extent of investigational medicinal product exposure and compliance

The extent of IMP exposure and compliance will be assessed and summarized within the recurrence population ([Section 2.3.2](#)).

2.4.3.1 Extent of investigational medicinal product exposure

The extent of IMP exposure will be assessed by the duration of IMP exposure and summarized for the recurrence population.

Duration of IMP exposure is defined as:

- Treatment duration (days) in a recurrence episode: date of last administration – date of first administration within the recurrence episode + 1 day.
- Total treatment duration (days): sum of the duration of treatment exposure.

Duration of IMP exposure will be summarized descriptively by analysis period and overall treatment period as a quantitative variable (number, mean, SD, median, minimum, and maximum).

Additionally, the number and percentage of participants with extension period in each recurrence episode will be provided.

Actual IMP exposure data, and derived data including total treatment duration, total number of study drug doses received, compliance, total corticosteroid treatment duration (days), and cumulative dose of corticosteroids by analysis period will be listed.

